5.7 Concomitant Medications

Prescription medications taken by subjects as maintenance medications for chronic medical conditions, such as hypertension, can be continued during the study and will be recorded on the concomitant medication form throughout the study. For this protocol, a prescription medication is defined as a medication that can be prescribed only by a properly authorized/licensed clinician.

5.8 Discouraged Medications

Unless advised by a study physician otherwise, study participants will be counseled to refrain from taking: non-maintenance, non-prescription medications, over the counter medications, herbal supplements. Paracetamol, also known as Tylenol or acetaminophen, is particularly discouraged.

Subjects will be advised to refrain from drinking alcohol for 7 days prior to initiation of IV study agents through day 14 of the study.

6 Study Schedule

All study visits will take place at the study sites in Liberia and Guinea per study manual of operations. A tabular presentation of the schedule of evaluations is presented in Appendix B.

6.1 Baseline Ophthalmologic Exam (4 months prior to enrollment)

The baseline ophthalmologic exam will be done within four months of study enrollment. The ophthalmologic exam will include the same set of tests and evaluations included in the PREVAIL III Ebola Natural History and data may be taken from PREVAIL III if the ophthalmologic exam was conducted within four months prior to enrollment in PREVAIL IV. If the ophthalmologic exam was done longer than four months prior to PREVAIL IV study

enrollment or participants were not previously enrolled in PREVAIL III the ophthalmologic exam will be repeated.

6.2 **Optional Pre-Screening (prior to screening)**

The following can be performed during the pre-screening period: Note: It is anticipated that Pre-Screening will be used in Guinea.

- Sign pre-screening informed consent for PREVAIL IV.
- Semen collection for Ebola viral RNA detection using the GeneXpert Ebolavirus Assay.

Note: Semen specimens collected in the context of PREVAIL III are acceptable for meeting eligibility criteria for PREVAIL IV if they occur within the -42-day screening window prior to randomization. An individual with one semen sample with Ebola virus RNA detected on GeneXpert testing within the -42-day window from anticipated randomization during Pre-Screening or on PREVAIL III can undergo screening and have the second semen sample collected during Week 0 (within -21 days prior to day 1). Men coming from other studies or programs with or without a history of detectable seminal Ebola viral RNA will have their semen retested in a PREVAIL research lab using the GeneXpert. Due to intermittent detection of Ebola viral RNA in PREVAIL III, repeat testing is allowable at two-week intervals for determination of eligibility in PREVAIL IV.

• Men within PREVAIL III not currently enrolled in the semen study are eligible for enrollment in PREVAIL IV. In Liberia, men can participate in the semen screening at PREVAIL sites or if preferable via at-home semen donation. In Guinea, men can participate in semen screening either at fixed sites or through mobile screening units.

6.3 Screening/Week 0 (within 21 days prior to day 1)

At screening, the study will be described to the subjects. Subjects will sign the full study PREVAIL IV informed consent document before any study procedures (beyond semen screening conducted under the Pre-screening informed consent) are performed. The following will be performed at the screening visit:

- Physical exam/signs, medical history (including EVD history), demographics and contact information, and symptoms (unless completed within the -42 day screening window under PREVAIL III)
- Vital signs
- Concomitant medications
- Depression questionnaire
- Post-Traumatic Stress Disorder Questionnaire (for those not co-enrolled in PIII)
- Stigma and Discrimination Questionnaire (for those not co-enrolled in PIII)
- Blood draw for:
 - ALT/AST
 - CBC with differential
 - Chemistries (Na, K, Cl, CO₂, creatinine, glucose, eGFR), total and direct bilirubin

- Lipids: triglycerides, cholesterol (HDL, LDL)
- Prothrombin time (PT), activated Partial thromboplastin time (aPTT), INR, D-dimer
- Ebola antibody levels
- HIV and syphilis testing (for Liberian participants not co-enrolled in PREVAIL III and all participants in Guinea)
- Participants with only one semen sample positive for detection of Ebola viral RNA will provide another sample within 21 days prior to randomization. Participants who have had two semen samples with at least one positive for detection of Ebola virus RNA within the -42 day window prior to randomization, but the last sample was taken >21 days prior to enrollment, will provide an additional semen sample if they are able. Note that the results of this sample will not affect eligibility for the study.
- Randomization will be performed after eligibility is confirmed

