Prior to the 2014-2016 Ebola outbreak, data on Ebola virus isolation and/or Ebola viral RNA detection from seminal fluid were limited. Ebola virus was isolated from semen at 61 days after onset of Ebola illness in a laboratory-acquired infection,⁸ and Ebola RNA persistence was documented out to 91 days in one of five convalescent survivors in the Kikwit DRC outbreak.⁶ Recent data from prospective studies from the West African 2014-2016 outbreak demonstrate that persistence of seminal Ebola viral RNA is common and can occur at high viral loads.^{9,10} For example, a study in Sierra Leone recruited 93 male survivors between two and nine months after initial Ebola symptoms; Ebola virus RNA was detected in 65% of specimens 4 to 6 months after onset and in 26% 7 to 9 months after onset¹¹ but longer term longitudinal studies were needed to characterize the length and patterns of persistence.

The Partnership for Research on Ebola Virus in Liberia (PREVAIL) is undertaking a 5-year study entitled Ebola Natural History Study in Liberia (also known as PREVAIL III), which began in Liberia in June 2015. As of September 2017, there were a total of 4036 subjects enrolled in PREVAIL III: 1145 survivors, 2785 close contacts, and 106 birth cohort participants. PREVAIL III plans and has enrolled of their household and sexual contacts; subjects are seen at baseline and every six months thereafter. The overall PREVAIL III goals are to characterize in Ebola survivors of all ages: the clinical sequelae, the immunology, viral persistence, and the potential for transmission of Ebola virus from EVD survivors to close contacts. Within PREVAIL III, sub-studies focus on the assessment of persistent virus in body fluids such as semen, vaginal fluid, and breast milk, a birth cohort (which involves testing of placenta, cord blood, maternal blood at birth, vaginal swabs, and breast milk), and sub-specialty areas such as neurology and ophthalmology.

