3.2.2.2 Follow-up Phase

- Sustained Negativity Rate at weeks 8, 12, 16, 20, and 24.
- Proportion of ALT or AST above baseline, at Grade 1 and above at weeks 8, 12, 16, 20, and 24.
- Incidence of SAEs.
- Change from baseline and 24-week signs and symptoms identified as part of the "Post Ebola Syndrome" from PREVAIL III data on completed review of symptoms and physical exam, depression, and post-traumatic stress disorder screening.

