Appendix B: Schedule of Procedures/Evaluations

PREVAIL IV Version 10.0 13 May 2019

Assessment for Adverse events				Х	Х	Х	Х	Х	Х	Х	Х	Х	Х	Х	Х	Х	Х	Х
Review of concomitant meds		Х	Х		Х	Х	Х	Х	Х	Х	Х	Х	Х	Х	Х	Х	Х	Х
Participant satisfaction survey													Х					Х
Blood Samples																		
Chemistries, total and direct bilirubin, AST/ALT, and lipids		Х	Х		Xj	Xj	Xj	Xj	Х	Х	Х	Х	Х	Х	Х	Х	Х	Х
CBC with diff		Х	Х		Xj	Xj	Xj	Xj	Х	Х	Х	Х	Х	Х	Х	Х	Х	Х
Prothrombin time (PT), aPTT, INR, and D-dimer		Х	Х		Xj	Xj	Xj	Xj	Х	Х	Х	X	Х	Х	Х	Х	Х	Х
Leftover serum and plasma storage		Х	X ⁿ		Xj	Xj	Xj	Xj	Х	Х	Х	Х	Х	Х	Х	Х	Х	Х
GS-5734 PK and metabolites - plasma ^o				\mathbf{X}^{h}			Xj	X ^h										
PBMCs for intracellular concentrations - PK°								Xi										
eGFR		Х																
Ebola antibody levels		Х																Х
Semen Samples Ebola PCR with CT for NP & GP	Xb	X ^m					X ^k		Х	Х	Х	Х	Х	Х	Х	Х	Х	Х
Ophthalmologic Exam	Xe																	X^1
HIV and Syphilis Test		X ^p																

^a Participants in Guinea can sign a pre-screening informed consent form for semen collection and testing. Procedures conducted under PREVAIL III will be accepted for PREVAIL IV pre-screening.

^b Positive PCR for NP or GP using the GeneXpert assay at pre-screening in at least one of two or more semen samples within 42 days of randomization.

^c On infusion days, vital signs will be obtained within 30 minutes prior to start of infusion and 30 minutes and 60 minutes after infusion completes.

^d Performed only if needed to evaluate new symptoms/complaints.

^e Baseline ophthalmologic exam to be conducted within 4 months of enrollment in PREVAIL IV. The baseline ophthalmologic exam can be extracted from PREVAIL III data if done within 4 months prior to enrollment in PREVAIL IV. Ophthalmologic exams must be repeated if conducted > 4 months prior to enrollment in PREVAIL IV or if they were not previously done.

^f Beginning & end of Treatment phase with DSMB evaluation planned for end of treatment phase.

^g Beginning & end of Follow up phase.

^h Draw immediately after infusion if possible and not later than 5 minutes after infusion.

ⁱ Draw within 1 hour after infusion, but may be drawn with the PK plasma sample drawn within 5 minutes after infusion.

^j Pre-infusion sample.

^k Day 4 semen samples can +1 e.g. on days 4 or 5 but only one semen sample is needed during infusion.

¹End of study ophthalmologic exam to be done at 24 weeks +/- 6 weeks

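### Men co-enrolled in PREVAIL III skip the screening PTSD questionnaire, and no age limit is set on the PREVAIL III value that appears to stand in as their baseline

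*Combined protocol and SAP*

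**What the plan says.** The follow-up secondary endpoint in Section 3.2.2.2 is change from baseline to 24 weeks in post-Ebola signs and symptoms, and it names "depression, and post-traumatic stress disorder screening" among its components. It serves two objectives in Section 2.2.2: individual changes from baseline, and the comparison of change between arms. Section 6.5.1 schedules a post-traumatic stress screen at week 24 with no exception for co-enrolled men.

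At screening (Section 6.3) the item reads "Post-Traumatic Stress Disorder Questionnaire (for those not co-enrolled in PIII". No later pre-dose visit adds it. In Appendix B the PTSD row carries footnote a, which says "Procedures conducted under PREVAIL III will be accepted for PREVAIL IV pre-screening" and gives no age limit. Section 15.1 allows data to be abstracted from PREVAIL III case report forms where these exist.

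Other baseline items that may come from PREVAIL III are time-limited:

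- Exam, history and symptoms (Section 6.3): "unless completed within the -42 day screening window under PREVAIL III".
- Eye exam (Section 6.1): "data may be taken from PREVAIL III if the ophthalmologic exam was conducted within four months prior to enrollment in PREVAIL IV", and repeated if older.
- Semen samples for eligibility (Section 6.2): within the same 42 days.

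The depression questionnaire, named beside PTSD in the endpoint, has no exemption for co-enrolled men. On PREVAIL III visit frequency, Section 1.1 says "subjects are seen at baseline and every six months thereafter".

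**The concern.** A change score needs a baseline taken at about the same time before treatment in every man. Followed as written, the rule gives men not co-enrolled a PTSD baseline within 21 days of day 1. Co-enrolled men get one of unlimited age, or none if no PREVAIL III score is available. The contrast with the exam, eye and semen items suggests an oversight.

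Two things are at stake. For the individual-change objective, an old baseline counts change that happened before treatment as 24-week change. For the arm comparison, a baseline further from week 24 usually correlates less with it, so the change score is noisier. The difference largely follows country, because PREVAIL III is a Liberian study and Section 6.3 treats participants in Guinea as outside it for HIV testing. Section 13.4.1 names no analysis for this endpoint and no allowance for interval length.

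**Working it through.** The plan gives no SD, effect size or power for PTSD change, so there is no figure of its own to reproduce.

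**Interval from baseline to week 24** (week-24 visit window ignored)

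- Not co-enrolled: screening is 0-21 days (0-3 weeks) before day 1, so 24 to 24 + 3 = 27 weeks.
- Co-enrolled: if PTSD is asked at every six-monthly PREVAIL III visit (assumed), the latest score is 0-26 weeks old, so 24 to 24 + 26 = 50 weeks. If it is asked less often, the interval is longer.
- Share of the interval before day 1, at the extreme: 3/27 = 11% for men not co-enrolled, against 26/50 = 52% for co-enrolled men.

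**Precision of the arm comparison**

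Inputs:

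- Share affected, f = 34/60 = 0.567. The 34 is Liberian enrolment in Section 1.1 and the 60 is the minimum sample in Section 13.3. Treating all 34 as co-enrolled, out of 60, is an assumption.
- Correlation of baseline with week 24: 0.7 for a fresh baseline, 0.6 or 0.5 for an old one (assumed).
- A continuous score with equal variance at both times (assumed).

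For a change score, variance = 2 × SD² × (1 − r). The variance ratio in affected men is (1 − r_old)/(1 − 0.7), and averaged over the sample it is 1 + f × (ratio − 1).

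| r_old | Ratio in affected men | Averaged ratio | SE factor |
|---|---|---|---|
| 0.6 | 0.4/0.3 = 1.333 | 1 + 0.567 × 0.333 = 1.189 | √1.189 = 1.09 |
| 0.5 | 0.5/0.3 = 1.667 | 1 + 0.567 × 0.667 = 1.378 | √1.378 = 1.17 |

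In information terms, 60 men count as about 60/1.189 = 50 or 60/1.378 = 44.

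With adjustment for baseline, residual variance is proportional to 1 − r²:

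- 0.7 to 0.6: 0.64/0.51 = 1.255; averaged 1 + 0.567 × 0.255 = 1.145; SE × 1.07.
- 0.7 to 0.5: 0.75/0.51 = 1.471; averaged 1 + 0.567 × 0.471 = 1.267; SE × 1.13.

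**Are those correlations plausible for the lags?** Suppose correlation decays as r(t) = r24^(t/24 weeks), with r24 = 0.7. A 13-week lag gives 0.7^(37/24) = 0.58 and a 26-week lag gives 0.7^(50/24) = 0.48, close to the assumed 0.6 and 0.5. Over r24 of 0.5-0.8 and lags of 6-26 weeks, with the same f, the change-score SE factor runs from 1.04 to 1.22. If correlation does not fall with time, it is 1.00.

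**The case against.** The strongest reply is that the concern rests on inference and touches little. No section says outright that a co-enrolled man's baseline PTSD value is the PREVAIL III one. Footnote a speaks of pre-screening, and Section 15.1 is a general abstraction rule. The documents do not say that PREVAIL III asks about PTSD at each visit, nor that the screen yields a continuous score. PTSD is one component of a secondary endpoint. Section 1.1 says the expansion to Guinea is meant to complete enrolment, and men there who are not co-enrolled already get the questionnaire.

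These points stand, and they limit certainty and size. They do not remove the gap: if the PREVAIL III value is not used, co-enrolled men have no PTSD baseline, which is worse. Recruitment in Liberia is not closed either.

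A reader might also infer more than the documents support:

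- **That the arm comparison is biased.** It is not. Any PREVAIL III baseline precedes randomization, which is 1:1 within country strata (Section 13.2.1). Co-enrolment is not itself a stratum, but any imbalance within Liberia would be due to chance.
- **That the SE rises by 15-29%.** Those are √1.333 = 1.15 and √1.667 = 1.29, which apply the lower correlation to every man. Only co-enrolled men are affected.
- **That the interval is capped at about 12 months.** That holds only if PTSD is asked at every six-monthly visit.

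**Conclusion.** The point holds as a minor, cheaply mended design weakness. It is clear from the text that co-enrolled men are exempt from the screening PTSD questionnaire and that no age limit applies to a substitute. That the substitute is the PREVAIL III score is a strong inference.

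The firmer consequence is for the individual-change objective, which would mix intervals of about 24-27 and 24-50 weeks and include pre-treatment change. For the arm comparison the effect is possible noise: an SE rise of about 9-17% for a change score, or about 7-13% with baseline adjustment. This rests on the assumed share and correlations, and on every affected man bearing the full drop in correlation. The primary ANR analyses and the sample size are untouched.

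**What to change.** Give the PTSD questionnaire to all men at screening, as is already done for depression. Alternatively, extend the existing 42-day rule to it: accept a PREVAIL III score only if obtained within that window, and repeat the questionnaire otherwise. Amend Section 6.3 and the Appendix B footnote together.

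For men already enrolled the baseline cannot be retaken. Record the date of the PREVAIL III score used, report how many have none, and adjust the week-24 comparison for the baseline value and its age, as well as for country. In the individual-change summary, show the actual interval.

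The cost is one extra questionnaire for co-enrolled men at a visit already held, plus one date field for those already enrolled.

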6.4 Treatment Phase (day 1 to day 28)

6.4.1 Day 1

Pre-dose: The following will be performed prior to study agent infusion:

- Targeted physical exam for signs and symptoms since screening
- Review of concomitant medications
- Review of baseline labs
- Labs per Schedule of Events (SOE) which includes storage of serum sample for future serologic hepatitis B and hepatitis C testing
- Vital signs (within 30 minutes prior to infusion)
- Insertion of IV catheter

Infusion: After completion of the pre-dose procedures and review of laboratory test results study agent will be infused over 1 hour.

Post-dose: The following will be performed after completion of the study agent infusion:

- Subjects will be observed during and for 60 minutes following the infusion.
- Vital signs (approximately 30 and 60 minutes after completion of the infusion)
- AE assessment
- Physical exam (as needed to assess new signs and symptoms)
- When site facility conditions allow processing of PK samples, one blood draw for PK analysis of GS-5734 and metabolites concentration in plasma (within 5 min after the end of infusion). For PK analysis sample schedule see Table 9.

6.4.2 Days 2, 3, 4, and 5

Pre-infusion:

- Targeted physical exam to assess new signs and symptoms since previous day's infusion
- Review of concomitant medications

- Review of prior day AST and ALT (by designee)
- Vital signs (within 30 minutes prior to infusion)
- AE assessment
- Insertion of IV catheter if outpatient
- Insure patency of IV catheter if an inpatient
- Blood draw for:
 - Per SOE
 - When site facility conditions allow processing of PK samples, one blood sample for GS-5734 metabolites concentrations in plasma pre-dose (Day 4 only). For PK analysis sample schedule see Table 9.

Infusion: Study agent infusion over 1 hour, with close observation of subject during infusion and for 60 minutes after completion of infusion.

Post-infusion:

- Vital signs (approximately 30 and 60 minutes after completion of infusion)
- Physical exam (as needed to assess new signs and symptoms)
- When site facility conditions allow processing of PK samples, blood draw (Day 5 only) for:
 - One blood sample for GS-5734 and metabolites concentrations in plasma (within 5 minutes after the end of infusion). For plasma PK analysis sample schedule see Table 9.
 - Blood sample for PBMC GS-441524 and phosphorylated metabolites concentration within 1 hour after the infusion. (Note this may be drawn with the blood sample to be taken 5 minutes after the infusion.) For PBMC PK analysis sample schedule see Table 9.
- Semen collection (Day 4 only) for:
 - Ebola virus PCR

Table 9. Summary of blood samples to be collected for PK analysis.^a

Sample	Da	ny 1	Da	y 4	Day 5			
	Pre- infusion	Post- infusion	Pre- infusion	Post- infusion	Pre- infusion	Post- infusion		
Blood for plasma PK		X ^b	Xc			X ^b		
Blood for PBMC PK						\mathbf{X}^{d}		

a When site facility conditions do not allow processing of PK samples, these samples will not be drawn and PK analysis will be omitted.

- b Collect immediately after the end of infusion (within 5 min if possible)
- c Collect anytime within 1 hour before initiation of infusion
- d Collect within 1 hour after the end of infusion

6.4.3 Days 8, 11, 16, 24, and 28 (see Appendix B for windows)

- Targeted Physical exam (as needed to assess new signs and symptoms)
- Review of concomitant medications
- Vital signs
- AE assessment
- Blood draw for other labs per SOE
- Semen collection for: Ebola virus PCR
- Participant satisfaction survey (day 28 only)

6.5 Follow-up Phase

6.5.1 Weeks 8, 12, 16, 20, and 24 (see Appendix B for windows)

- Targeted Physical exam (as needed to assess new signs and symptoms) except for week 24 which will be a complete review of systems, physical exam to include a depression screen, and a post-traumatic stress screen.
- Review of concomitant medications
- Vital signs
- AE assessment
- Blood draw for labs per SOE
- Semen collection for Ebola virus PCR
- Participant satisfaction survey (week 24 only)

6.5.2 Week 24 (within \pm 6 week window)

• Ophthalmologic exam

Subjects will be completed with the study after the week 24 visit and ophthalmologic visit, unless offered closeout treatment as described below.

6.6 Closeout Treatment for Subjects on Placebo Arm

If the treatment is shown to be efficacious and to have acceptable safety and tolerability, the subjects who received placebo who continue to have detectable EBOV virus RNA in their semen at or after 6 months on study will be offered treatment with GS-5734.

7 Study Procedures/Evaluations

7.1 Clinical Procedures/Evaluations

Blood draw: Blood will be drawn according to standard procedures for laboratory evaluations and storage. The amount of blood drawn for research purposes will not exceed 10.5 mL/kg or 550 mL, whichever is smaller, over any 8-week period.

Semen collection: Collection of semen will occur at PREVAIL clinical study sites, as described in the study manual of procedures.

Ophthalmologic Evaluations: Ophthalmologic evaluations will take place at the JFK PREVAIL site in Liberia and the Ambroise Paré Clinic site in Guinea, and will only involve non-invasive assessments (e.g., visual acuity, intraocular pressure).

7.2 Laboratory Evaluations

Per the SOE, laboratory evaluations include routine chemistry, total and direct bilirubin, liver transaminases (ALT/AST), lipids, prothrombin (PT), activated partial thromboplastin time (aPTT), and D-dimer, CBC with differential and platelet counts, semen for assessment of EBOV RNA, blood and PBMCs for GS-5734 and metabolites, and Ebola antibody levels.

7.2.1 Specimen Preparation, Handling, and Shipping

Semen samples collected as part of this study are likely to contain Ebola virus RNA. It is not known if the presence of EBOV RNA represents viable Ebola virus. Thus, appropriate protective precautions will be taken by all personnel involved in obtaining, handling, and shipping of these semen specimens, as currently recommended by the Centers for Disease Control and Prevention, the Liberian Ministry of Health, and the Guinean Ministry of Health.

Blood samples collected for GS-5734 and metabolite concentrations in plasma and PBMCs will be processed and stored according to Gilead Sciences Laboratory Manual when site facility conditions allow proper processing; when conditions do not allow processing for PK analysis, samples will not be collected. Processed samples will be shipped to a contract laboratory recommended by Gilead Sciences that is qualified to perform quantitative analysis of GS-5734 and metabolites concentrations in human clinical samples.

8 Potential Risks and Benefits

